3.1.1.2 Treatment Period

Arm 1 (patients who received QCC374 in the companion QCC374X2201 study):

Arm 1 consists of a treatment period of 720 days. Subjects may be dispensed study drug for the extension study no earlier than Day -1. The first study drug administration for the QCC374X2201E extension study will occur on Day 1. The first study drug administration may occur at home if the patient was dispensed study drug on Day -1.

Subjects will continue to receive QCC374 at the same dose that was administered during the proof of concept study (0.06 mg bid or lower if their individual maximum tolerated dose (MTD) if their individual MTD was below 0.06 mg bid). At any point during the treatment period, if a subject is on 0.06 mg and the investigator believes, based on their medical judgement, that the dose should be reduced due to the severity of adverse events, the investigator may reduce the dose to 0.03 mg. The investigator may subsequently increase the dose back to the 0.06 mg dose if the investigator believes this is appropriate based on their medical judgement. A follow-up phone call should be scheduled 7 days after adjustment to review safety and tolerability of the dose adjustment.

Visits will occur every three months during the extension treatment period, but the subject may need to return for drug resupply on a monthly basis. The resupply plan is country and site specific, and the expectations for resupply should be reviewed with the subject prior to the first dispensing of study medication.

Arm 2 (patients who received placebo in the companion QCC374X2201 study):

Arm 2 consists of a treatment period of 720 days, which is further divided into a Titration Period (Day 1 to Day 14), a Stable Dose Period (Day 15 to Day 112), and an Extension Treatment Period (Day 113 to Day 720) (Figure 3-1). Subjects in Arm 2 will be dispensed study drug on Day 1, and the first study drug administration for the QCC374X2201 extension study will occur on Day 1. This study drug administration must occur in the clinic.

Arm 2 Titration Period:

The starting dose of QCC734 for subjects in Arm 2 is 0.03 mg bid.

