- On Day 7 the investigator will assess the subject's clinical status, and reported adverse events. The subject's dose will be increased to 0.06 mg unless the investigator believes, based on their medical judgement, that the dose should not be increased due to the severity of typical pharmacological effects of IP-receptor agonists, such as headache, jaw pain, myalgia, flushing and nausea.
- On Day 14 the investigator will assess the subject's clinical status, and reported adverse events. If the subject is not receiving the maximum 0.06 mg bid dose, the dose level will be increased to 0.06 mg, unless the investigator believes, based on their medical judgement, that the dose should not be increased due to the severity of adverse events. If this dosing scenario occurs, the subject is allowed to continue in the trial, and will continue to receive 0.03 mg bid.
- Following the Day 14 visit no further up-titrations above the Day 14 dose are allowed. On Day 21, if the subject was up-titrated on Day 14, a follow-up phone call visit will occur to review safety and tolerability.

Arm 2 Stable Dose Period:

During the stable dose period (Day 15 to Day 112), subjects will continue to receive the QCC374 dose established during the Titration Period (0.06 mg or 0.03 mg). At any point during the stable dose period, if a subject is on 0.06 mg and the investigator believes, based on their medical judgement, that the dose should be reduced due to the severity of adverse events, the investigator may reduce the dose to 0.03 mg. The investigator may subsequently increase the dose back to the 0.06 mg dose if the investigator believes this is appropriate based on their medical judgement. A follow-up phone call should be scheduled 7 days after adjustment to review safety and tolerability of the dose adjustment. During the stable dose period the subject will return for safety assessments every 28 days.

Arm 2 Extension Period:

Once the stable dose period is complete (following Day 112), subjects will continue to receive the same dose of QCC374 throughout the extension treatment period. Visits will occur every three months during the extension treatment period, but the subject may need to return for drug resupply on a monthly basis. The resupply plan is country and site specific and the expectations should be reviewed with the subject prior to the first dispensing of study medication.

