9.1 Adverse events

An AE is any untoward medical occurrence (i.e., any unfavorable and unintended sign [including abnormal laboratory findings], symptom or disease) in a subject or clinical investigation subject *after providing written informed consent* for participation in the study. Therefore, an AE may or may not be temporally or causally associated with the use of a medicinal (investigational) product.

The occurrence of adverse events should be sought by non-directive questioning of the subject at each visit during the study. AEs also may be detected when they are volunteered by the subject during or between visits or through physical examination, laboratory test, or other assessments.

Abnormal laboratory values or test results constitute adverse events only if they fulfill at least one of the following criteria:

- they induce clinical signs or symptoms,
- they are considered clinically significant,
- they require therapy.

Clinically significant abnormal laboratory values or test results should be identified through a review of values outside of normal ranges/clinically notable ranges, significant changes from baseline or the previous visit, or values which are considered to be non-typical in patients with underlying disease. Investigators have the responsibility for managing the safety of individual subject and identifying adverse events. Alert ranges for liver related events are included in [Section 9.3](#).

Adverse events must be recorded on the Adverse Events CRF for subjects that have been randomized into the study. The adverse events should be reported according to the signs, symptoms or diagnosis associated with them, and accompanied by the following information:

- The severity grade:
 - mild: usually transient in nature and generally not interfering with normal activities
 - moderate: sufficiently discomforting to interfere with normal activities
 - severe: prevents normal activities
- Relationship to the study treatment
- Duration (start and end dates) or if the event is ongoing, an outcome of not recovered/not resolved should be reported.
- Whether it constitutes a serious adverse event (SAE). See [Section 9.2](#) for definition of SAE.
- Action taken regarding study treatment. All adverse events should be treated appropriately. Treatment may include one or more of the following:
 - no action taken (i.e. further observation only)
 - study treatment dosage adjusted/temporarily interrupted

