7.2 Descriptive analyses

Subject demographics and other baseline characteristics

All data for background and demographic variables will be listed by arm and subject. Baseline characteristics will be presented both at Core (QCC374X2201) and Extension study (QCC374X2201E1) baseline. The Extension baseline, is defined, as the Extension study screening visit where the respective measurements are available (as per the assessment schedule) and Day 112 of the Core study where they are not. Summary statistics will be provided by arm.

Relevant medical history, current medical conditions, results of laboratory screens, drug tests and any other relevant information will be listed by treatment group and subject.

Treatment

Data for study drug administration (rescue medication) and concomitant therapies will be listed by arm and subject.

Summary tables will be used to present the proportion of subjects who reached each QCC374 dose, the proportion of subjects who had their dose reduced due to an adverse event, and the proportion of subjects who completed 16 weeks of treatment by dose subject received most from Day 15 to Day 112. Summary statistics for the number of days at each dose will be provided.

Vital signs

All vital signs data will be listed by treatment, subject, and visit/time and if ranges are available abnormalities (and relevant orthostatic changes) will be flagged. Summary statistics will be provided by arm and visit/time.

ECG evaluations

All ECG data will be listed by treatment, subject and visit/time, abnormalities will be flagged. Summary statistics will be provided by arm and visit/time.

Clinical laboratory evaluations

All laboratory data will be listed by treatment, subject, and visit/time and if normal ranges are available abnormalities will be flagged. A separate listing is provided presenting all parameters in a subject with any abnormal values. Summary statistics will be provided by arm and visit/time.

Adverse events

All information obtained on adverse events will be displayed by arm and subject.

The number and percentage of subjects with adverse events will be tabulated by body system and preferred term with a breakdown by arm. A subject with multiple adverse events within a body system is only counted once towards the total of this body system and arm.

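### The adverse event table by arm pools Days 1-112, when Arm 2 is seen more often than Arm 1, with long-term follow-up, and should also be shown by onset period

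*SAP*

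**What the plan says.** SAP 7.2 (Adverse events) states: "The number and percentage of subjects with adverse events will be tabulated by body system and preferred term with a breakdown by arm". Protocol 11.4.4 describes the same table by core-study treatment, which defines the arms. Protocol section 11 runs the analysis on all data when the trial ends. None of these places divides events by onset period or comments on how often each arm is seen. Protocol 3.2 names the number of participants with AEs as the primary endpoint, so this table carries it.

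On detection, Protocol 9.1 says: "The occurrence of adverse events should be sought by non-directive questioning of the subject at each visit during the study". It adds: "AEs also may be detected when they are volunteered by the subject during or between visits", and it also allows detection through examinations and tests.

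On visits, Protocol 3.1.1.2 says for Arm 1: "Visits will occur every three months during the extension treatment period, but the subject may need to return for drug resupply on a monthly basis". Resupply arrangements depend on country and site. For the first dose in Arm 2 it says: "This study drug administration must occur in the clinic". It continues: "On Day 7 the investigator will assess the subject's clinical status, and reported adverse events" and "On Day 14 the investigator will assess the subject's clinical status, and reported adverse events". A Day 21 call follows if the dose was raised on Day 14. Then: "During the stable dose period the subject will return for safety assessments every 28 days". Table 8-2 puts those visits on Days 28, 56, 84 and 112, with three-monthly assessments from Day 180.

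**The concern.** If asking is one of the ways AEs are found, the arm that is asked more often will tend to show more of them. Protocol 3.5.2 expects prostacyclin-type reactions to be mild to moderate and transient. A headache or flushing that lasted a day or two is easier to lose at a visit three months later than at one two weeks later.

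The denser Arm 2 schedule covers the same weeks as that arm's first dosing and titration. Arm 1 went through its own initiation in the core study, outside this table. The Arm 2 column therefore combines intensive questioning, first exposure and long-term follow-up, while the Arm 1 column is long-term follow-up only. A reader comparing the two columns of the primary table cannot tell which of these produced a difference.

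**Working it through.** The documents give no visit count or ratio, so there is no figure of the plan's own to reproduce. I counted visits from the schedule.

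**Inputs**

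- Arm 2 by Day 112 (Protocol 3.1.1.2, Table 8-2): Days 1, 7, 14, 28, 56, 84 and 112 = 7 clinic visits. The conditional Day 21 call makes 8 contacts.
- Arm 2 after Day 112 (Table 8-2): assessments on Days 180, 270, 360, 450, 540, 630 and 720 = 7, plus EOS on Day 750 = 8. Counting every monthly dispensing visit from Day 150 to 720: (720 - 150)/30 + 1 = 20, plus EOS = 21.
- Arm 1, three-monthly (Protocol 3.1.1.2): Days 90 to 720 = 720/90 = 8, plus EOS = 9. One falls by Day 112 and 8 after it. Counting monthly returns: 720/30 = 24, plus EOS = 25, of which 3 fall by Day 112 and 22 after it. The Table 8-1 columns before Day 570 were not available in the text I worked from, so the earlier days are inferred. The later columns show assessments on Days 630 and 720 and dispensing every 30 days.
- Arm 1 Day 1: SAP 1.4 describes a Day 1 visit in both arms. Protocol 3.1.1.2 lets the first Arm 1 dose be taken at home if drug was dispensed on Day -1. I counted it both ways.

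**Ratios, Arm 2 : Arm 1**

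| Arm 1 counted as | By Day 112 | After Day 112 | Whole study |
|---|---|---|---|
| Three-monthly only | 7:1 = 7.0 | 8:8 | 15:9 = 1.67 |
| Three-monthly plus Day 1 | 7:2 = 3.5 | 8:8 | 15:10 = 1.5 |
| Monthly returns, no Day 1 | 7:3 = 2.33 | 21:22 | 28:25 = 1.12 |
| Monthly returns plus Day 1 | 7:4 = 1.75 | 21:22 | 28:26 = 1.08 |

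With the Day 21 call the first column becomes 8.0, 4.0, 2.67 and 2.0. Leaving Day 1 out of both arms, with three-monthly visits, gives 6:1 = 6.0. The direction is the same in every row, and the imbalance lies before Day 112.

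**Illustration of what this could mean for capture.** Assume that a subject asked at a visit reports every mild event from the 14 days ending on that visit and none from before.

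- Arm 2, Days 1-112: the windows cover Days 1-14, 15-28, 43-56, 71-84 and 99-112, so 70/112 = 62.5%.
- Arm 1, Day 1 plus Day 90: (1 + 14)/112 = 15/112 = 13%.
- Arm 1, Day 1 plus monthly returns: 1 + 3 x 14, plus the 6 days (107-112) covered by the Day 120 return, so 49/112 = 44%.

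The gap is 70/15 = 4.7-fold or 70/49 = 1.4-fold. With 90-day recall all three figures are 100% and the gap vanishes.

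**The case against.** The strongest reply is that the plan makes no comparison to bias. Protocol 11.4.2 rules out inferential analysis, 6.3 says the study is not randomized, 3.3 says there is no comparator, and the aim in 11.4 is long-term safety. This stands to the extent that no test or estimate is invalid. But the table is broken down by arm, and readers will compare the columns.

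Three further points limit the size. The table covers the whole study, where the ratio is far smaller than by Day 112. Each subject counts once per body system, so repeated asking matters less once an event has been recorded. Protocol 9.1 also allows events to be volunteered between visits or found on testing, and it does not rank visit questioning above those routes. All three stand.

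Timing is also recoverable, because AE start dates are collected and everything is listed by arm and subject. That stands, but a listing is not a summary.

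A reader might infer that Arm 2 is questioned seven times as often as Arm 1. The documents do not support that as a single figure. It requires counting Day 1 in Arm 2 but not in Arm 1, and assuming no questioning at resupply returns. The documents do not say whether those returns include questioning: the AE row of the schedule says only that it is done as required.

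A reader might also infer that an Arm 2 excess would be an artefact of the schedule. That is not supported either. The extra visits coincide with first dosing and titration, so a true initiation effect would look the same.

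**Conclusion.** The point holds as a cheap improvement to the AE summary. Under every way of counting, Arm 2 is seen more often by Day 112, by a factor of about 1.75 to 7, and the pooled table does not show where that period ends. Over the whole study the factor is about 1.1 to 1.7. After Day 112 the assessment visits match.

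The range rests on three unknowns: the inferred Arm 1 schedule, whether Arm 1 has a Day 1 visit, and whether resupply returns include AE questioning. The effect on AE counts cannot be estimated from the documents, and the recall figures only show how strongly the answer depends on the assumed recall window. Splitting by onset period confines the mixture to a labelled table but does not resolve it.

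**What to change.** In SAP 7.2, keep the whole-study AE and serious adverse event tables and add:

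- AE tables by arm for onset on Days 1-112 and for onset from Day 113 to EOS. The denominator for each is the safety-set subjects still in follow-up at the start of that period.
- A footnote to the Days 1-112 table saying that visit frequency differs between arms and that ascertainment cannot be separated from a true initiation effect in Arm 2.
- A footnote to the later table saying that assessment visits match (8 in each arm including EOS) but that only subjects who remained in the study are included.

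This needs only AE onset dates, which are already collected, and changes nothing in conduct. SAP 7.2 already uses Day 112 as a boundary in its dose summaries. The downside is two more tables with small cells: the Protocol synopsis expects approximately 30 subjects in total to complete the core study, split over two arms.

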Study design	
This is a multicenter, open label trial to assess the safety, tolerability pharmacokinetics and efficacy of inhaled QCC374 over a two year period in patients with PAH who have completed study QCC374X2201. This study will have two arms. In Arm 1, patients who had been randomized to active in the QCC374X2201 study will continue on QCC374 at their highest stable dose. In Arm 2, the patients who had been randomized to placebo will complete a titration scheme similar to that of the active arm in QCC374X2201 protocol.
 
For both arms the study consists of a screening visit, a treatment period of 720 days, and an EOS visit 30 days after treatment is completed. This study may be amended in the future to increase the treatment duration period, as additional data emerges for QCC374 in PAH.
 
All patients willing to participate in this trial will roll-over directly from the QCC374X2201 study after their 112 days of participation has been completed. The electrocardiogram (ECG), pulse oximetry, vital signs, weight, spirometry, 6MWD, Corporate Confidential Information hematology, blood chemistry, body measurement and urinalysis results from the QCC374X2201 Visit Day 111 visit will be used as the baseline assessments for the extension study.

Population	The study population will be comprised of male and female PAH patients who have completed the QCC374X2201 PoC study and wish to participate in the extension study. A total of approximately 38 subjects are planned to be enrolled and randomized in the QCC374X2201 study, with approximately 30 patients expected to complete the study.
Key Inclusion criteria	
 • Written informed consent must be obtained before any assessment is performed. • Subject was enrolled in the QCC374X2201 study and completed per protocol
Key Exclusion criteria	
 • Subjects who have started receiving prostacyclin (epoprostenol), prostacyclin analogs (i.e. trepostinil, iloprost, beraprost) or prostacyclin receptor agonists (i.e. selexipag) since the last study drug intake in the QCC374X2201 study. • Females who are pregnant, or who plan to become pregnant during the study, or who are breastfeeding • Any known factor or disease that may interfere with treatment compliance or study conduct (i.e. drug or alcohol dependence) • Subjects who withdrew consent from the study QCC374X2201

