3.1 Study design

This is a multicenter, open label trial to assess the safety, tolerability, pharmacokinetics and efficacy of inhaled QCC374 over a two year period, in subjects with PAH who have completed study QCC374X2201. This study will have two arms (Figure 3-1). In Arm 1, subjects randomized to active in the QCC374X2201 study will continue on QCC374 at their highest stable dose. In Arm 2, the subjects randomized to placebo in the QCC374X2201 study will complete a titration scheme similar to that of the active arm in QCC374X2201 protocol. For subjects in both Arms, the assessments obtained during the Day 111 visit for the companion QCC374X2201 study (including physical examination, vital signs, pulse oximetry, ECG, spirometry, 6MWD, **Corporate Confidential** and laboratory data) will be used as the baseline values for this study. **Information**

[figure not shown]
This study may be amended in the future to increase the treatment duration period, as additional data emerges for QCC374 in PAH.

Figure 3-1 QCC374X2201E1 Extension Study Design

Arm 1

Arm 2

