4.1 Inclusion criteria

Subjects eligible for inclusion in this study must fulfill **all** of the following criteria:

1. Written informed consent must be obtained before any assessment is performed.
2. Subject was enrolled in the QCC374X2201 study and completed per protocol.
3. For patients enrolling in Arm 2, the spirometry assessed at Visit 111 in the companion QCC374X2201 study must meet ATS criteria for acceptability and reproducibility. If necessary, this assessment can be repeated during the Screening Period.

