If local regulations deviate from the contraception methods listed above and require more extensive measures to prevent pregnancy, local regulations apply and will be described in the ICF.

Women are considered post-menopausal and not of child bearing potential if they have had 12 months of natural (spontaneous) amenorrhea with an appropriate clinical profile (e.g. age appropriate, history of vasomotor symptoms) or have had surgical bilateral oophorectomy (with or without hysterectomy), total hysterectomy or tubal ligation at least six weeks ago. In the case of oophorectomy alone, only when the reproductive status of the woman has been confirmed by follow up hormone level assessment is she considered not of child bearing potential.

6. Subjects who demonstrated a serious protocol deviation, determined by the Sponsor or Investigator, related to subject compliance in the study QCC374X2201.

No additional exclusions may be applied by the investigator, in order to ensure that the study population will be representative of all eligible patients.

NOTE: Re-screening of subjects is not allowed for anything other than the Spirometry assessment for inclusion. This assessment will be over read by a central reader and results will need to be communicated from the vendor to the site staff prior to treatment for subjects in Arm 2 in the extension study. If the subject does not meet inclusion from the Day 111 spirometry, the subject is allowed to repeat the assessment during the screening window. The repeat assessment will also need to be over read by the central vendor and the results will need to be confirmed to the site staff.

5 Restrictions for Study Subjects

During recruitment, screening/informed consent review, and baseline visit, the subjects must be informed and reminded of the restrictions outlined in this section.

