Physical examination		X			X			X			X			X	X
Pulse oximetry		X			X			X			X			X	X
Vital Signs		X			X			X			X			X	X
Pregnancy test		X ³			X ³			X ³			X ³			X ³	X ³
Body weight															X
Blood chemistry		X			X			X			X			X	X
Hematology		X			X			X			X			X	X
Urinalysis		X			X			X			X			X	X
Spirometry		X			X			X			X			X	X
ECG evaluation		X			X			X			X			X	X
6-Minute Walk Test		X			X			X			X			X	X
		X			X			X			X			X	
Corporate Confidential Information		X			X			X			X			X	
														X	
														X	
														X	
Echocardiogram															
Corporate Confidential Information								X							

Epoch	Extension-Treatment ^{8,9}															
Visit Name	Long Term Follow Up													EOS (30 days post last treatment visit)		
Visit Numbers ¹	419	420	421	422	423	424	425	426	427	428	429	430	431	432	433 ⁸	
Study Day(s)	330 ±5	360 ±5	390 ±5	420 ±5	450 ±5	480 ±5	510 ±5	540 ±5	570 ±5	600 ±5	630 ±5	660 ±5	690 ±5	720 ±5	750 ±5	
Time (post-dose)	-	-	-	-	-	-	-	-	-	-	-	-	-	-	-	
Drug dispensation	X	X	X	X	X	X	X	X	X	X	X	X	X	X		
Study drug administration	Study drug administration will be bid - refer to Section 3.1 and Site Operations Manual															
PK blood collection	See Table 8-3 below															
Concomitant medications	As required															
Adverse events	As required															
Serious adverse events	As required															
Comments	As required															
Study/epoch completion information															X	X

¹ Visit structure given for internal programming purpose only

² The earliest that informed consent can occur is Day 111 in the companion QCC374X2201 study, and informed consent can occur no later than 7 days after Day 111.

³ Urine Pregnancy Test (females only)

⁴ Spirometry assessment during screening is only required if the spirometry testing session for V111 in the QCC374X2201 study did not meet ATS criteria for acceptability and reproducibility.

⁵ Domiciling is optional. The subject should remain in the clinic until all assessments are complete.

⁶ Assessments to be completed immediately prior to first QCC374 administration.

⁷ Assessments to be repeated prior to dosing if more than 4 days have elapsed since the D111 QCC374X2201 assessments.

⁸ If a patient stops study medication prematurely, at a minimum, a safety evaluation must be completed. Then an attempt should be made to complete all assessments listed under Visit 433, with the investigator making the determination of what is safe and feasible to complete.

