For the legal requirements of ClinicalTrials.gov and EudraCT, two required tables on treatment emergent adverse events which are not serious adverse events with an incidence greater than 5% and on treatment emergent serious adverse events and SAE suspected to be related to study treatment will be provided by system organ class and preferred term on the safety set population.

If for a same patient, several consecutive AEs (irrespective of study treatment causality, seriousness and severity) occurred with the same SOC and PT:

- a single occurrence will be counted if there is ≤ 1 day gap between the end date of the preceding AE and the start date of the consecutive AE
- more than one occurrence will be counted if there is > 1 day gap between the end date of the preceding AE and the start date of the consecutive AE.

For occurrence, the presence of at least one SAE / SAE suspected to be related to study treatment / non SAE has to be checked in a block e.g., among AE's in a ≤ 1 day gap block, if at least one SAE is occurring, then one occurrence is calculated for that SAE.

The number of deaths resulting from SAEs suspected to be related to study treatment and SAEs irrespective of study treatment relationship will be provided by SOC and PT.

Other safety evaluations

Spirometry

All spirometry data will be listed by subject and visit/time. Summary statistics (raw values primarily, and change from baseline) will be provided by QCC374X2201 study arm and visit/time.

Baseline is defined as the Day 112 of the Core study for the subjects who received QCC374 in the Core study, and the Screening visit of the Extension study for the subjects who received placebo in the Core study.

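### SAP 7.2 takes the Arm 2 spirometry baseline from an extension Screening test that the protocol requires only after a failed Core V111 session, and gives no fallback

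*SAP*

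**What the plan says.** The spirometry paragraph of SAP 7.2 plans these outputs: "Summary statistics (raw values primarily, and change from baseline) will be provided by QCC374X2201 study arm and visit/time". It then defines baseline separately by arm. For subjects treated with QCC374 in the Core study (Arm 1) it is Core Day 112. For the others (Arm 2) the definition continues: "and the Screening visit of the Extension study for the subjects who received placebo in the Core study". No rule follows for an Arm 2 subject who has no Screening spirometry.

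The protocol makes that test conditional in three places:

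- Table 8-2, footnote 4: "Spirometry assessment during screening is only required if the spirometry testing session for V111 in the QCC374X2201 study did not meet ATS criteria".
- Section 4.1, criterion 3: "For patients enrolling in Arm 2, the spirometry assessed at Visit 111 in the companion QCC374X2201 study must meet ATS criteria". A repeat during screening is available if necessary.
- Section 4.2, closing note: "If the subject does not meet inclusion from the Day 111 spirometry, the subject is allowed to repeat the assessment during the screening window".

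The protocol also names a different baseline. Section 3.1 begins "For subjects in both Arms, the assessments obtained during the Day 111 visit for the companion QCC374X2201 study", gives a list "including physical examination, vital signs, pulse oximetry, ECG, spirometry, 6MWD", and says that these serve as the baseline values. The synopsis agrees: "results from the QCC374X2201 Visit Day 111 visit will be used as the baseline assessments for the extension study". SAP 1.4 likewise carries Core spirometry into the extension for all patients, though it labels the Core visit Day 112.

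**The concern.** The SAP ties the Arm 2 baseline to a test that most of the arm may never have. A subject whose V111 session was acceptable has no required Screening spirometry. Without an optional test, that subject has no baseline under SAP 7.2 and drops out of the change-from-baseline summary.

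The subjects who remain are a selected group. If sites do only what the schedule requires, the Arm 2 summary describes only people whose V111 session failed on test quality. Arm 2 is the arm starting QCC374 in this study, and protocol 3.5.3 names spirometry as the objective monitor for bronchospasm, so this output bears on the primary safety objective.

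**Working it through.** The documents state no figure on this point, so there is nothing to reproduce. The check compares the texts and then works out the share affected.

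**1. Who has the required test.** By Table 8-2 footnote 4, criterion 3 and the note in 4.2, Screening spirometry is required in Arm 2 only after a V111 session that failed ATS criteria.

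**2. Can V111 count as the Screening test?** Protocol 3.1.1.1 allows extension consent only after all Core Day 111 assessments are complete. Footnote 4 makes one test depend on the result of the other. They are therefore separate sessions.

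**3. Is there a Day 1 pre-dose value to use instead?** SAP 7.2 names none. The spirometry row of Table 8-2, as far as its layout can be read, shows none, although the column alignment is uncertain.

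**4. Share of Arm 2 without a baseline.** Let f be the share whose V111 session failed ATS criteria, and s the share of the others who are given an optional Screening test. Then:

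- no baseline = (1-f)(1-s)
- V111 failures among those with a baseline = f / (f + (1-f)s)

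The documents give neither f nor s. Since each can lie anywhere from 0 to 1, the first share can lie anywhere from 0% to 100%. The values below are assumptions for illustration.

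| s | f | No baseline | V111 failures among those with a baseline |
|---|---|---|---|
| 0 | 5% | 0.95 × 1 = 95% | 100% |
| 0 | 10% | 0.90 × 1 = 90% | 100% |
| 0 | 20% | 0.80 × 1 = 80% | 100% |
| 0 | 30% | 0.70 × 1 = 70% | 100% |
| 50% | 10% | 0.90 × 0.5 = 45% | 0.10/0.55 = 18% |
| 50% | 30% | 0.70 × 0.5 = 35% | 0.30/0.65 = 46% |
| 100% | any | 0% | f |

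**5. In subjects.** The synopsis expects about 30 Core completers but does not give the allocation. Assuming that one third to one half are in Arm 2 gives n = 10 to 15. With s = 0, the expected number with a baseline is n × f. That runs from 10 × 0.05 = 0.5 to 10 × 0.30 = 3.0 when n = 10, and from 15 × 0.05 = 0.75 to 15 × 0.30 = 4.5 when n = 15. The chance that nobody has a baseline is (1-f)^n. At f = 10% this is 0.90^10 = 0.349 for n = 10 and 0.90^15 = 0.206 for n = 15.

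**6. Under a corrected rule.** Take V111 if it met ATS criteria, otherwise the acceptable Screening repeat. Criterion 3 requires one of these for entry to Arm 2, so the share of eligible subjects without a baseline is 0% at any f and s.

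**7. Day labels.** SAP 1.4, SAP 6.1.1 and SAP 7.2 (under baseline characteristics and again under spirometry) refer to Core Day 112. Protocol 3.1 and the synopsis refer to Core Day 111, and protocol 3.1.1.1 uses the two as different days.

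**The case against.** The strongest reply is that the SAP already contains the missing rule. Under demographics and baseline characteristics, SAP 7.2 defines the Extension baseline as the Screening visit where a measurement exists there and the Core visit where it does not. SAP section 2 lists FEV1% predicted among those characteristics, so the rule already reaches one spirometry measure. SAP 1.4 also points to the Core value. The spirometry sentence could then be a shortened form of the general rule. This makes a drafting slip plausible, but it does not resolve the conflict: the spirometry paragraph has its own arm-specific definition, which sets Core against extension Screening and would be redundant if the general rule governed.

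A second reply is that screening may open on Day 111 and an acceptable V111 session satisfies the screening requirement, so V111 could be assigned to the Screening visit. That gives the right answer, but the SAP does not say so, and the protocol treats the two sessions as distinct.

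Three points on this side stand:

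- The percentages at s = 0 only restate 1-f for assumed values of f, so they illustrate the mechanism and do not measure its impact.
- Whether Core Day 111 and Day 112 are one visit or two depends on the Core schedule, which is not in these documents. The label mismatch is a separate matter to reconcile and does not support the main point.
- The consequence is narrow. Raw values are primary in the SAP, and all spirometry is listed. Protocol 11.4.4 plans no change from baseline. Protocol 11.4.2 rules out inference and already puts Core baseline and end-of-study values in the summary tables. The bronchospasm discontinuation criterion in protocol 7.2 does not use this baseline.

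**Conclusion.** The concern holds. The Arm 2 spirometry baseline in SAP 7.2 conflicts with protocol 3.1, the synopsis, Table 8-2 footnote 4 and SAP 1.4. As written, it leaves change from baseline undefined for Arm 2 subjects with an acceptable V111 session and no optional Screening test.

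The size of the gap cannot be fixed from the documents. It vanishes if every Arm 2 subject has a Screening test. If only required tests are done, it covers all of Arm 2 except the V111 failures. It affects one descriptive safety summary; adverse event tables and per-subject monitoring are untouched. The point should be fixed before database lock. It does not threaten the study's conclusions.

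**What to change.** In the spirometry paragraph of SAP 7.2, define the Arm 2 baseline as the Core V111 session, replaced by the Screening repeat when V111 did not meet ATS criteria. Keep the Core value for Arm 1. State the same replacement rule in protocol 3.1, which does not say whether a repeat supersedes a failed Day 111 session. Reconcile Core Day 111 in the protocol with Core Day 112 in SAP 1.4, 6.1.1 and 7.2, so that one visit carries the baseline flag.

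For the SAP, the cost is a one-sentence edit, a label check and a change to the baseline flag in programming, all before database lock. Stating the rule in the protocol as well would go through its amendment process. No new data are needed, because criterion 3 already ensures an acceptable session for every eligible Arm 2 subject.
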